4.3.1 Downloading Site Registration Documents

Site registration forms may be downloaded from the A011203 protocol page located on the CTSU members' website. Permission to view and download this protocol and its supporting documents is restricted and is based on person and site roster assignment housed in the CTSU RSS.

- Go to <https://www.ctsu.org> and log in to the members' area using your CTEP-IAM username and password
- Click on the Protocols tab in the upper left of your screen
- Either enter the protocol # in the search field at the top of the protocol tree, or
- Click on the By Lead Organization folder to expand
- Click on the NCTN - Alliance link to expand, then select trial protocol #A021202
- Click on the Site Registration Documents link
- Click on LPO Documents, select the Site Registration documents link, and download and complete the forms provided

4.3.2 Requirements for A011203 Site Registration

- CTSU Transmittal Sheet (optional)
- IRB approval (For sites not participating via the NCI CIRB; local IRB documentation, an IRB-signed CTSU IRB Certification Form, Protocol of Human Subjects Assurance Identification/IRB Certification/Declaration of Exemption Form, or combination is accepted)

4.3.4 Checking Your Site's Registration Status

You can verify your site registration status on the members' section of the CTSU website.

- Go to <https://www.ctsu.org> and log in to the members' area using your CTEP-IAM username and password
- Click on the Regulatory tab at the top of your screen
- Click on the Site Registration tab
- Enter your 5-character CTEP Institution Code and click on Go

Note: The status given only reflects compliance with IRB documentation and institutional compliance with protocol-specific requirements as outlined by the Lead Network. It does not reflect compliance with protocol requirements for individuals participating on the protocol or the enrolling investigator's status with the NCI or their affiliated networks.

4.4 Pre-registration Requirements

- Patient pre-registration can occur only after screening evaluation is complete, pre-registration eligibility criteria have been met, and the study site is listed as "approved" in the CTSU RSS.
- **Informed consent:** the patient must be aware of the neoplastic nature of his/her disease and willingly consent after being informed of the procedure to be followed, the experimental nature of the therapy, alternatives, potential benefits, side-effects, risks, and discomforts. Current human protection committee approval of this protocol and a consent form is required prior to patient consent and pre-registration.

4.5 Patient Pre-Registration Procedures

Patient enrollment will be facilitated using the Oncology Patient Enrollment Network (OPEN). OPEN is a web-based registration system available on a 24/7 basis. To access OPEN, the site user must have an active CTEP-IAM account (check at < <https://eapps-ctep.nci.nih.gov/iam/index.jsp>>) and a 'Registrar' role on either the LPO or participating organization roster.

All site staff will use OPEN to enroll patients to this study. It is integrated with the CTSU Enterprise System for regulatory and roster data and, upon enrollment, initializes the patient in the Rave database. OPEN can be accessed at <http://open.ctsu.org> or from the OPEN tab on the CTSU members' side of the website at <https://www.ctsu.org>. A user manual is available for OPEN users on the CTSU site.

Following the Pre-registration, and prior to registration/randomization (days -28 to -1 see Section [5.1](#) and [5.2](#)), a standard of care biopsy of metastatic breast tissue must be taken for local pathologic review. Of note, if the patient has had a recent biopsy (within 28 days prior to pre-registration) of metastatic breast tissue after the most recent progression, this sample can substituted for local pathological review for determination of ER, PR and HER2 status.

For patients who have consented to the correlative tissue studies, additional tissue cores will be obtained at the time of the pre-registration biopsy (see Sections [6.2.2](#) and [6.2.3](#)).

If the local pathology assessment finds that the patient **does not** have ER positive, HER2 negative disease, the CRA will enter the Alliance ID number obtained at pre-registration; upload a copy of the local pathology report, de-identified (but including the patient's Alliance ID number) into RAVE for documentation of estrogen receptor and HER2 status; and complete the end of pre-registration phase case report form. The patient will not proceed to registration or randomization. No further follow-up is required. Research tissue cores need not be submitted. Future treatment is at the discretion of the patient's medical team.

4.6 Patient Registration/Randomization procedure

If the local pathology assessment finds that the patient **does** have ER positive, HER2 negative disease, CRA will enter the Alliance ID number obtained at pre-registration and the stratification factors into the OPEN registration system and obtain a treatment assignment. The CRA will also enter the Alliance ID number obtained at pre-registration; upload a copy of the local pathology report, de-identified (but including the patient's Alliance ID number), into RAVE for documentation of estrogen receptor and HER2 status; complete the end of pre-registration phase case report forms as well as the baseline patient status case report forms and submit the research tissue cores.

4.7 Registration to Correlative and Companion Studies

4.7.1 Registration to Substudies described in Section [14.0](#)

There are four substudies within Alliance A011203. These correlative science studies **must be offered to all patients** enrolled on Alliance A011203 (although patients may opt to not participate). These substudies do not require separate IRB approval. The substudies included within Alliance A011203 are:

- Evaluation of *ESRI* alterations and markers of endocrine resistance in patients treated with either tamoxifen or Z-Endoxifen HCl Alliance A011203-ST1, (Section [14.1](#))
- Circulating tumor cells and circulating cell free DNA, A011203-ST2 (Section [14.2](#))
- Biochemical markers of bone turnover, Alliance A011203-ST3 (Section [14.3](#))
- Z-Endoxifen HCl and tamoxifen pharmacokinetics and pharmacogenetics, Alliance A011203-PP1 (Section [14.4](#))

If a patient answers “yes” to “Question #1” in the model consent, they have consented to participate in the substudy described in Section [14.1](#), the patient should be registered to Alliance A011203-ST1. If a patient answers “yes” to “Question #2” in the model consent, they have consented to participate in the substudy described in Sections [14.2](#), [14.3](#) and [14.4](#), and the patient should be registered to Alliance A011203-ST2, A011203 ST3 and A011203-PP1. Patients should be registered to the correlative studies at the same time they are registered to the treatment trial (A011203).

4.8 Stratification Factors and Treatment Assignments

Endocrine resistant disease

- 1) Primary endocrine resistant disease*
- 2) Secondary endocrine resistant disease**

Prior CDK 4/6 inhibitor and/or everolimus

- 1) Prior CDK 4/6 inhibitor or everolimus or both
- 2) No prior CDK 4/6 inhibitor and no prior everolimus

Disease type

- 1) Measureable by RECIST criteria
- 2) Bone only disease

*Primary endocrine resistant disease is defined as one of the following:

- Recurrence within the first 2 years of adjuvant endocrine therapy while on aromatase inhibitor therapy
- Progression within the first 6 months of initiating first-line endocrine therapy (either aromatase inhibitor or fulvestrant containing regimen) for the treatment of metastatic breast cancer.

**Secondary Clinical Resistance is defined as one of the following:

- Recurrence after year 2 while receiving adjuvant aromatase inhibitor therapy, or within 12 months of completing adjuvant aromatase inhibitor therapy.
- Progression occurring 6 or more months after initiating the first endocrine therapy for metastatic disease (either fulvestrant or aromatase inhibitor containing regimens).

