3.2 Pre-registration Eligibility Criteria

3.2.1 Women who agree to undergo a standard of care core biopsy of recurrent or metastatic breast cancer (see Section 6.2.2 for details of biopsy) to confirm the ER+ ($\geq 10\%$ nuclear staining) and HER2 negative status (see Sections [3.3.5](#) and [3.3.6](#)).

3.2.2 Patient must have been previously treated with an aromatase inhibitor (either letrozole, anastrozole or exemestane) either in the adjuvant or metastatic setting, and have one of the following types of primary or secondary endocrine resistant disease.

Primary Clinical Resistance is defined as one of the following:

- Recurrence within the first 2 years of adjuvant endocrine therapy while on aromatase inhibitor therapy
- Progression within first 6 months of initiating first-line endocrine therapy (either aromatase inhibitor or fulvestrant containing regimen) for the treatment of metastatic breast cancer.

Secondary Clinical Resistance is defined as one of the following:

- Recurrence after year 2 while receiving adjuvant aromatase inhibitor therapy, or within 12 months of completing adjuvant aromatase inhibitor therapy.
- Progression occurring 6 or more months after initiating the first endocrine therapy for metastatic disease (either fulvestrant or aromatase inhibitor containing regimen).

3.2.3 Patients with a history of measurable disease as defined by RECIST criteria (See Section [11.0](#)) or bone only disease are eligible. Note: Those patients with non-measurable disease and bone metastases are eligible.

3.2.4 No history of tumors involving spinal cord or heart.

___ 3.2.5 No current evidence of visceral crisis or lymphangitic spread.

___ 3.2.6 No known brain metastases.

___ 3.2.7 Women age \geq 18 years.

___ 3.2.8 **Women must be postmenopausal**

Postmenopausal status is verified by:

- Prior bilateral surgical oophorectomy, or
- Age \geq 60 years, or
- Age $<$ 60 with no menses for $>$ 1 year with FSH and estradiol levels within postmenopausal range, according to institutional standard.

___ 3.2.9 **Prior treatment**

- No more than two prior chemotherapy regimens in the metastatic setting.
- Prior treatment with an aromatase inhibitor (either anastrozole, letrozole or exemestane), either in the adjuvant or metastatic setting is required.
- Unlimited prior endocrine regimens in the metastatic setting, which may have included everolimus or a CDK4/6 inhibitor (such as a palbociclib, abemaciclib or ribociclib) containing regimens.

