3.3 Registration Eligibility Criteria

Registration must be completed within 28 days of Pre-registration

3.3.1 Patients with either measurable disease as defined by RECIST criteria (See Section 11.0) or bone only disease are eligible. Note: Those patients with both non-measurable disease and bone metastases are eligible.

- Non-measurable bone only disease: Non-measurable bone only disease may include any of the following: blastic bone lesions, lytic bone lesions without a measurable soft-tissue component, or mixed lytic-blastic bone lesions without a measurable soft-tissue component.
- Lytic bone lesions, with an identifiable soft tissue component, evaluated by CT or MRI, can be considered as measurable lesions if the soft tissue component otherwise meets the definition of measurability previously described.

3.3.2 No tumors involving spinal cord or heart.

3.3.3 No visceral crisis, lymphangitic spread or known brain metastases: Visceral crisis is not the mere presence of visceral metastases, but implies severe organ dysfunction as assessed by symptoms and signs, laboratory studies, and rapid progression of disease.

3.3.4 Histologic confirmation, from the A011203 Pre-registration biopsy, by institutional/local pathologist of either locally advanced or metastatic breast cancer that is estrogen receptor positive and HER2 negative.

Those patients with bone only disease with either no tumor or insufficient tumor for ER/PR and HER2 staining after the bone biopsy are still eligible to participate in this study.

3.3.5 Estrogen receptor positive disease is defined as > 10% nuclear staining.

3.3.6 **HER2 Negative Disease as per 2013 ASCO/CAP guidelines, one of the following must apply:**

- 1) 0 or 1+ by IHC and not amplified by ISH
- 2) 0 or 1+ by IHC and ISH not done
- 3) 2+ by IHC and not amplified by ISH or
- 4) IHC not done and not amplified by ISH

3.3.7 **None of the following therapies are allowed prior to registration*:**

- Chemotherapy \leq 2 weeks
- Immunotherapy \leq 2 weeks
- Biologic therapy \leq 2 weeks
- Hormonal therapy \leq 2 weeks
- Monoclonal antibodies \leq 2 weeks
- Radiation therapy \leq 2 weeks
- Anti-Her-2 or other “targeted” (e.g. mTOR) therapy \leq 2 weeks

*Note: Any toxicities derived from these therapies must be \leq grade 2 prior to starting study therapy.

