13.0 STATISTICAL CONSIDERATIONS**13.1 Study Design**

A randomized phase II clinical trial design was chosen to assess whether Z-Endoxifen HCl shows promise in providing greater in antitumor activity (in terms of increasing progression-free survival) than tamoxifen in postmenopausal women with metastatic ER positive breast cancer that is endocrine resistant.

This study will use a dynamic allocation procedure to allocate an equal number of patients to each of the treatment arm. This procedure will balance the marginal distributions of the stratification factors between these treatment arms. The stratification factors that will be used are: prior palbociclib and/or everolimus, type of disease and degree of endocrine resistance (see Section [4.8](#)).

All patients meeting the eligibility criteria who have signed a consent form and have begun treatment will be evaluable for assessment of all of the clinical endpoints. Patients will be included in the treatment group they were randomized to regardless of their actual treatment or duration of treatment. Summary statistics for patient and tumor characteristics, eligibility rates, length of follow-up, and treatment acceptance rates will be calculated by assigned treatment arm.

13.1.2 Definition and documentation of primary endpoint.

The primary endpoint is progression-free survival (PFS) defined as the time from randomization to documentation of local, regional or distant disease progression or death without progression of disease.

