13.1.6.2 Tumor Response Rate by study arm

The tumor response rate is defined as the 100% time the number of patients with a CR or PR (as defined by the RECIST criteria) on 2 consecutive evaluations at least 6 weeks apart divided by the total number of eligible patients who began study treatment. A 90% binomial confidence interval will be constructed for the true response rate.

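### The response rate in 13.1.6.2 counts patients who cannot have a partial response, and the disease-type stratum in 4.8 has no level for one eligible group

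*Combined protocol and SAP*

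**What the plan says.** **Response.** Objective 2.2.2 asks whether the RECIST response rate differs between the randomized arms. Section 13.1.6.2 counts patients with CR or PR on two consecutive evaluations at least 6 weeks apart, "divided by the total number of eligible patients who began study treatment", and plans a 90% binomial interval.

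**Disease type.** Section 4.8 has two levels: measurable by RECIST, and bone only. Section 3.3.1 admits both groups and adds a third: "Those patients with both non-measurable disease and bone metastases are eligible". Section 3.2.3 carries a similar note, and 7.3 names the third group separately when it describes crossover.

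**Resistance.** In 4.8 each level is met by one of an adjuvant or a metastatic criterion.
- Primary: "Recurrence within the first 2 years of adjuvant endocrine therapy while on aromatase inhibitor therapy", or "Progression within the first 6 months of initiating first-line endocrine therapy".
- Secondary: recurrence after year 2 on an adjuvant AI or within 12 months of completing it, or "Progression occurring 6 or more months after initiating the first endocrine therapy for metastatic disease".

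**Prior targeted therapy.** Level 1 in 4.8 is "Prior CDK 4/6 inhibitor or everolimus or both". Section 13.1 reads: "The stratification factors that will be used are: prior palbociclib and/or everolimus, type of disease and degree of endocrine resistance", and then refers the reader to 4.8.

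**The concern.** A response rate is easiest to interpret when every patient in the denominator could respond. Here the denominator includes patients for whom RECIST partial response is not defined. The reported rate in each arm then depends on case mix as well as drug activity, and a reader comparing it with other RECIST rates would see too low a figure.

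The stratum gap is a separate matter. Site staff enter the factors at registration (4.6), and the dynamic allocation in 13.1 balances the levels they enter. A patient with, say, a pleural effusion and bone metastases fits neither disease-type level, so different sites may code her differently. The same applies, less often, to a patient who meets both resistance definitions. Balance on the intended factors is then less well assured in a trial of 40 per arm.

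**Working it through.** **1. The plan's own design figure.** Inputs from 13.1.3: one-sided alpha 0.10, power 95%, hazard ratio 0.5, 1:1 allocation.

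Events (Schoenfeld) = 4 × (1.2816 + 1.6449)² / (ln 0.5)² = 4 × 8.564 / 0.4805 = 71.3, rounded up to **72**, as stated. With 72 events the power is 95.1%. Exponential PFS with medians of 3 and 6 months, 15 months of uniform accrual and 9 months of follow-up gives 38.6 + 33.3 = 71.9 expected events from 80 patients. No input to this calculation depends on the strata or on the response definition.

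**2. Can a patient without measurable disease be a responder?**
- Target lesions are chosen from measurable lesions (11.4.1).
- PR is a 30% fall in a sum taken over target lesions and nodes (11.4.3.2). With no target lesion there is no sum, so PR cannot occur.
- Non-measurable sites are non-target (11.4.2), and 11.4.3.3 defines a non-target CR when all such lesions disappear.
- The overall-status table in 11.4.4 is limited to measurable disease, and 11.4.5 gives bone-only patients a progression rule. Nothing converts a non-target CR into an overall status.

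So PR is unavailable and the route to an overall CR is undefined.

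**3. Size of the dilution.** Let f be the share without measurable disease, r_m the response rate in measurable disease and r_n the rate in the rest.

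Reported rate = (1 − f) × r_m + f × r_n

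The documents give neither f nor r_m. Assume r_m = 20% and r_n = 0:

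| f (assumed) | Reported rate |
|---|---|
| 10% | 0.90 × 20% = 18% |
| 20% | 0.80 × 20% = 16% |
| 25% | 0.75 × 20% = 15% |
| 40% | 0.60 × 20% = 12% |

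If f is equal in both arms, the between-arm difference is also multiplied by (1 − f) and the ratio of rates is unchanged. If f differed (assumed 20% against 40%), equal 20% activity would read as 16% against 12%.

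**4. Interval width.** With 40 in an arm, f = 25% and 6 responders, exact 90% intervals are:
- all treated: 6/40 = 15% (6.7% to 27.5%)
- measurable disease: 6/30 = 20% (9.1% to 35.7%)

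**5. Disease type.** Three groups are eligible and two levels exist. A third level would raise the factor combinations from 2 × 2 × 2 = 8 to 2 × 2 × 3 = 12. Widening level 2 keeps them at 8.

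**6. Resistance.** Recurrence at 18 months on an adjuvant AI, followed by progression 10 months into first-line fulvestrant, is primary by the adjuvant criterion and secondary by the metastatic one. The reverse order of labels is also possible. Progression at exactly 6 months can be read into either level. No text says which criterion decides.

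**The case against.** **The denominator matches the objective.** Objective 2.2.2 concerns patients as randomized, and an all-treated denominator is close to that. Section 13.1.6.2 plans an interval, not a test between arms. Disease type is itself a balancing factor, so the dilution should be similar in both arms. All of this stands. It makes the measurable-disease rate an addition to the all-patient rate, not a replacement.

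**Stronger readings a reader might infer.** The documents do not support these:
- *Patients without measurable disease have only a progression rule, so they are non-responders by definition.* Sections 11.4.2 and 11.4.3.3 give them a lesion-level CR. The gap is the missing overall status and the impossibility of PR.
- *Non-measurable disease plus bone has no progression rule, so PFS is undefined for it.* The same sections define progression there by new lesions or unequivocal worsening, in substance the bone-only rule of 11.4.5.
- *The allowance in 3.2.9, "Unlimited prior endocrine regimens in the metastatic setting, which may have included everolimus or a CDK4/6 inhibitor", multiplies the resistance overlap.* Both metastatic criteria are tied to the first line, so later lines create none. The overlap is between adjuvant AI failure and first-line metastatic failure.
- *The resistance levels do not fit the patients admitted.* Section 3.2.2 uses the same definitions as 4.8, so every eligible patient meets at least one level.
- *The CDK4/6 factor is ambiguous at registration.* Section 13.1 defers to 4.8, which is explicit. The narrower drug name looks like leftover wording.

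**Conclusion.** The response point holds. The rate in 13.1.6.2 understates activity in measurable disease by a factor of about (1 − f). On assumed values, a 20% rate reads as 16% at f = 20% and 12% at f = 40%. The range for f and the 20% rate are illustrations, because the documents give neither.

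The missing disease-type level also holds as a textual gap. The documents do not say how many patients fall into it, or how many meet both resistance definitions, so no size can be put on the loss of balance. Any resulting imbalance is chance, not bias. The resistance tie-break and the CDK4/6 wording are lesser points.

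It would be wrong to infer that the primary result is at risk. Section 13.1.5 describes a generalized log-rank test with no stratification, so miscoded strata do not enter it. The 72 events, 80 patients and stated power are unchanged.

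**What to change.** 1. **13.1.6.2:** report the response rate with its 90% interval, by arm, among patients with measurable disease at baseline, alongside the all-patient rate. The cost is a somewhat wider interval (working, step 4).
2. **4.8, disease type:** relabel level 2 as *non-measurable disease (bone only, or bone plus other non-measurable disease)*, and edit the registration screen to match.
3. **4.8, resistance:** state one precedence rule for patients who meet both definitions. The most recent qualifying failure is one option among several.
4. **13.1:** change the wording to *CDK4/6 inhibitor and/or everolimus*, as in 4.8.

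None of this adds patients, procedures or events. The practical cost lies in coding. Section 13.1.3 records 81 patients enrolled by November 2016, of whom 24 were ineligible, leaving up to 81 − 24 = 57 who may already carry a level entered under the current text. Where the factors are used in analysis, the resistance rule should be applied in the same way to patients already randomized, so that two codings are not mixed.

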4.9 Re-registration at the Time of Progression

Patients who meet the RECIST criteria for disease progression during tamoxifen treatment may switch to Z-Endoxifen HCl until disease progression is documented. Please note that patients who opt to cross over must be re-registered to the study within 14 days of progression documentation.

Re-registration procedures:

OPEN may be accessed at <https://open.ctsu.org>, from the OPEN tab on the CTSU website at <https://www.ctsu.org>.

To enroll a patient within OPEN, institution staff must have:

1. A valid and active CTEP-IAM account. This is the same user ID and password used for CTSU's website (for more information see https://www.ctsu.org/public/CTEP-IAM_Factsheet.pdf).
2. Enrollment of patients on Alliance A011203 coordinated protocols requires a "Registrar" role in the ALLIANCE roster. Assignment of the "Registrar" role is managed through the Alliance Central Office.

The OPEN system will provide the registering site with a printable confirmation of re-registration. Please print the confirmation for your records. Further instructional information is provided on the CTSU members' website OPEN tab, or within the OPEN URL. For any additional questions, contact the CTSU Help Desk at [name], or [contact].

